1.6 Clinical Studies

There have been no prior studies of GB-102 in subjects with DME or RVO.

A single IVT injection Phase 1/2a clinical study with GB-102 in subjects with nAMD has been completed and results are provided in the Investigator's Brochure.

1.7 Study Rationale for Protocol GBV-102-003

The purpose of this study is to assess the safety and pharmacodynamics of a single injection of 2 dose levels of GB-102 (1 mg, 2 mg) in subjects with a known diagnosis of macular edema secondary to DME or RVO who have been treated with at least three prior injections of any anti-VEGF agent (aflibercept, bevacizumab, or ranibizumab) and shown evidence of a prior response to anti-VEGF treatment.

1.8 Compliance

This study will be conducted in compliance with this protocol, and in accordance with ICH guidelines, Good Clinical Practice (GCP), the Declaration of Helsinki, and will comply with the obligations and requirements of the Sponsor as listed in Title 21 of the US Code of Federal Regulations (CFR).

2 OBJECTIVES

2.1 Primary Objective

To evaluate the safety and tolerability of a single intravitreal injection of two different dose strengths of GB-102 (1 mg, 2 mg) in subjects with macular edema secondary to diabetic retinopathy or retinal vein occlusion who have received prior treatment with anti-vascular endothelial growth factor (VEGF)

2.2 Secondary Objectives

To evaluate the pharmacodynamic response as measured by best corrected visual acuity (BCVA) and central subfield thickness (CST) and time to first rescue injection.

3 INVESTIGATIONAL PLAN

3.1 Overall Study Design Summary

This is a Phase 2a, multicenter, open-label, single injection, parallel arm, non-controlled safety, tolerability and pharmacodynamics study.

Eligible subjects will be consecutively enrolled to 1 of 2 concurrently initiated open-label GB-102 treatment arms ([Appendix 18.1](#)):

Group 1: 1 mg (50 μ L) (N=10)

Group 2: 2 mg (50 μ L) (N=10)

GB-102 will be administered on Day 1 in both Cohorts ([Table 3-1](#)). Subjects will return to the study center on Days 14, 30, 60, 90, 120, 150, and 180 for safety and clinical assessments. Subjects will exit the study following all study assessments on Day 180.

The safety parameters to be collected include adverse events (AEs) and serious adverse events (SAEs), physical examination, vital signs, BCVA using the Early Treatment of Diabetic Retinopathy Study (ETDRS) protocol, slit-lamp biomicroscopy findings, intraocular pressure (IOP) measurements, dilated ophthalmoscopy results, and date of administration of rescue treatment.

Pharmacodynamic activity will be assessed by means of BCVA (using the ETDRS Protocol), retinal central subfield thickness (CST) using spectral-domain optical coherence tomography (SD-OCT), and color fundus photography (CFP) (including wide field fundus photography, if available).

Safety Monitoring

The medical monitor will evaluate the on-going safety data in this open-label study.

Masking

This is an open-label study and the injecting investigator/physician may be the assessing investigator. The SD-OCT and CFP technicians and other site personnel, the Sponsor, and CRO are unmasked to treatment assignment.

Rescue Treatment

Rescue treatment (any anti-VEGF agent; aflibercept, bevacizumab, or ranibizumab) will be permitted in the study eye in *any* of the study arms if the qualifying criteria are met for rescue treatment.

3.2 Study Design Rationale

The proposed study is designed to assess the safety and pharmacodynamics of a single injection of 2 dose levels of GB-102 (1 mg, or 2 mg) administered in subjects with DME/macular edema

due to RVO who have demonstrated a prior response to at least 3 prior injections of any IVT anti-VEGF agent.

The medical monitor will evaluate masked safety data on an on-going basis.

The planned study assessments (eg, AEs, abbreviated physical examinations, clinical laboratory tests, vital sign measurements, BCVA assessments, IOP, slit-lamp biomicroscopy examinations, SD-OCT, CFP (including wide field of view imaging, if available), dilated ophthalmoscopy evaluations) are conventional parameters used to evaluate the safety and pharmacodynamic activity of pharmacologic agents in retinal disease.

The sample size of this study was not selected to support specific statistical hypothesis testing. A sample size of approximately 20 evaluable subjects in the SS analysis set allows for detection of adverse events rates that exceed 15% overall and exceed 30% for each dose with approximately 95% confidence.

Rescue treatment (any anti-VEGF agent; aflibercept, bevacizumab, or ranibizumab) for the study eye is within the standard-of-care for subjects with DME/macular edema due to RVO for the maintenance of visual acuity and/or the prevention of vision loss.

3.3 Appropriateness of Measurements

The primary aim of the data analyses in this study is to assess the safety, tolerability and pharmacodynamics of a single IVT injections of GB-102 in subjects with DME/macular edema due to RVO who have shown prior response to IVT anti-VEGF agents.

The safety, tolerability and pharmacodynamic parameters to be evaluated in this study are consistent with landmark, randomized, multicenter, registrational drug studies of IVT agents used to treat DME and RVO ([Nguyen 2010](#), [Campochiaro 2010](#)).

Table 3-1. Study Plan and Schedule of Assessments

Activity/Assessment	S ^a	B	W 2	M 1	M 2	M 3	M 4	M 5	M 6 (ET)
Visit Day ± Window ^b	-30 to -3	1	14±2	30±4	60±7	90±7	120±7	150±7	180±7
Informed Consent/HIPAA	X								
Inclusion/Exclusion Criteria	X								
Demographics Data	X								
Medical/Medication History	X								
Physical Examination	X								X
Pregnancy Testing ^c	X	X				X			X
Clinical Laboratory Tests ^d	X								
Adverse Events	X	X ^e	X	X	X	X	X	X	X
Concomitant Medications	X	X	X	X	X	X	X	X	X
Vital Signs ^f	X	X							X
BCVA (ETDRS) ^g	OU	OU	OU	OU	OU	OU	OU	OU	OU
Slit-lamp Biomicroscopy	OU	OU	OU	OU	OU	OU	OU	OU	OU
IOP ^h	OU	OU	OU	OU	OU	OU	OU	OU	OU
Dilated Ophthalmoscopy	OU	OU	OU	OU	OU	OU	OU	OU	OU
SD-OCT ⁱ	OU	OU	OU	OU	OU	OU	OU	OU	OU
Intravitreal Depot Photography ^j		SE	SE	SE	SE	SE	SE	SE	SE
GB-102 Injection ^k		SE							
Postinjection Assessment ^l		SE							
Follow-Up Call ^e		+1 day							

B = Baseline Visit; BCVA = best corrected visual acuity; ET = Early Termination; ETDRS = Early Treatment Diabetic Retinopathy Study; HIPAA = Health Insurance Portability and Accountability Act; IOP = intraocular pressure; M = month; OU = both eyes; S = Screening Visit; SD-OCT = spectral domain-optical coherence tomography; SE = study eye; V = visit; W = week

- a Screening Visit to occur 3 to 30 days before study baseline (Day 1) to ensure that laboratory results are obtained. Imaging eligibility based on SD-OCT will be investigator determined; there is no reading center confirmation.
- b The protocol-specified procedures for a given study visit may be split across 2 days within the visit-specific window (if applicable); however, for each visit, all BCVA, ophthalmic examinations, and ophthalmic imaging must be performed on the same day and cannot be split across 2 or more days. Evaluations should be performed by the same evaluator for the same subject throughout the study whenever possible. If it is not possible to use the same evaluator to follow the subject, then evaluations should overlap (examine the subjects together and discuss findings) for at least 1 visit.
- c Urine pregnancy test in women of childbearing potential only; additional pregnancy tests may be performed at any time/day during the study.
- d **Chemistry** (non-fasting blood): hemoglobin A1c.
- e All subjects will receive a telephone call for the day after the intravitreal injection to assess for any significant complaints or adverse events.

- f Heart rate, blood pressure; additional collection of height (without shoes) will be measured at Screening and body weight will be measured at Screening and Month 6/exit.
- g Visual acuity assessment using ETDRS protocol at 4 m with manifest refraction will be performed at all visits; 1 m may be performed if needed.
- h Goldmann applanation tonometry or Tono-Pen acceptable; however, technique used at baseline must be used at all subsequent visits. Intraocular pressure will be checked before dilation and the IVT injection of study drug at the dosing visit (Baseline [Day 1]).
- i Measurements for CST determined by the investigator (no central reading center confirmation)
- j Wide field color fundus photography (eg, Optos Ultra-widefield or Zeiss Clarus 500 or other ultra-widefield equipment) of the intravitreal GB-102 depot will be obtained following the dilated ophthalmic examination at all visits – if available at the study site. The initial images of the depot should be obtained at baseline (Day 1) *after* the IVT injection of GB-102 and conducted through (and include) the final study visit and any unscheduled visits. The photographs may be used to document the general appearance and rate of bioabsorbability of the depot. If no wide-FOV camera available, standard 30-degree field of view (FOV) imaging documenting the visual axis will be sufficient. For detailed instructions regarding collection of the intravitreal depot CFP imaging, refer to the separately provided guideline.
- k Following intravitreal injection of GB-102, the subject should remain seated for approximately 15 minutes post-injection with minimal to no movement of the head (e.g., bending over, shaking head, laying down) and avoid significant eye movement.
- l Postinjection assessment to consist of checking for count fingers or hand motion vision within 15 minutes after injection; if needed, subject can be examined (eg, additional IOP assessment or ophthalmoscopy, per discretion of the investigator) prior to going home.

4 SUBJECT POPULATION

4.1 Number of Subjects and Subject Selection

Subjects eligible for screening must have the diagnosis of macular edema secondary to DME or RVO in the **study eye** that was diagnosed in the 6 weeks to 24 months prior to screening and treated with at least 3 prior IVT injections of an anti-VEGF agent (aflibercept, bevacizumab, or ranibizumab) and demonstrated a response to prior treatment within 16 weeks of initial diagnosis and treatment. Subjects must have the most recent anti-VEGF agent administered within 42 days of screening. Eligibility will be determined by the investigating physician based upon his/her interpretation of SD-OCT evaluation of the disease. There is no third-party reading center confirmation of any imaging parameters in this study.

The complete inclusion and exclusion criteria are presented, respectively, in [Sections 4.3](#) and [4.4](#).

The study is planned to be conducted at approximately 4 to 6 study centers in the US.

4.2 Study Eye Determination

The **study eye** is defined as the eye that meets all the inclusion criteria and none of the exclusion criteria. If both eyes meet the inclusion and exclusion criteria, the eye with the worst visual acuity at Baseline will be selected. If both eyes have the same baseline visual acuity, the right eye will be selected.

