GB-102 is lyophilized and reconstituted with hyaluronic acid prior to intravitreal administration to produce an administered IVT dose of 1 mg or 2 mg sunitinib in a 50 µL injection using a 27-gauge needle. Subjects will receive their assigned dose (1 mg or 2 mg GB-102) on Day 1 as a single IVT injection.

**Reference Therapy,
Dose, and Mode of
Administration:**

No reference therapy is provided in this study (ie, there is no active control arm)

Study Endpoints:

Primary Safety Endpoint

- Occurrence of ocular and non-ocular adverse events and serious adverse events at all study visits

Secondary Pharmacodynamic Endpoints

- BCVA (ETDRS protocol) at all study visits
- CST (SD-OCT) at all study visits
- Observed subjects rescue-free at each study visit

Statistical Methods:

Analysis Population

- **Safety analysis set (SS):** Includes all subjects who receive a dose of study treatment. Subjects who receive rescue treatment during the study will be included in the SS. Subjects will be analyzed according to actual treatment received.
- **Full analysis set (FAS):** Includes all subjects who receive a dose of study treatment, and complete the baseline and at least one post-baseline visit. All data collected from subjects who receive rescue treatment during the study will be included in the FAS. Subjects will be analyzed according to their assigned treatment regardless of actual treatment received.
- **Per protocol analysis set (PP):** Consists of a subset of the FAS and includes subjects with no major protocol violations that would affect the assessment of the pharmacodynamics and rescue data. Data collected after the receipt of rescue therapy during the study will not be included in PP analyses.

Safety Endpoint Analyses

All reported adverse events will be coded using the Medical Dictionary for Regulatory Activities (MedDRA). Treatment-emergent adverse events (TEAEs) will be summarized by system organ class (SOC) and preferred term (PT). Frequencies and percentages will be provided by treatment group for subjects with TEAEs, treatment related TEAEs, serious TEAEs, serious treatment related TEAEs, TEAEs leading to premature study discontinuation and TEAEs by maximum severity. Separate analyses will be performed for ocular AEs in the study eye, ocular AEs in the non-study eye, and nonocular AEs.

The SS will be the primary population used for analysis of the primary safety endpoint.

Pharmacodynamic Endpoint Analyses

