6.2 Study Visit Procedures

6.2.1 Screening (Day -30 through Day -3)

The Screening Visit should occur 3 to 30 days before study Baseline (Day 1) to ensure that laboratory results are obtained and the investigator has confirmed eligibility. The following procedures are to be performed at this visit:

- Obtain informed consent and authorization
- Collect demographic information and medical and ophthalmic history
- Collect information about concomitant medications and procedures
- Conduct a physical examination
- Draw blood samples for hemoglobin A1c
- Conduct a urine pregnancy test on women of childbearing potential (note that additional pregnancy tests may be performed at any time/day during the study)
- Obtain vital signs (blood pressure, heart rate, height [without shoes] and weight)
- Assess BCVA (using the ETDRS protocol with manifest refraction) in both eyes
- Perform the slit-lamp biomicroscopy of both eyes
- Measure IOP (via Goldmann applanation tonometry or Tono-Pen) in both eyes (the same measurement method should be used throughout the study)
- Perform dilated ophthalmoscopy of both eyes
- Obtain SD-OCT imaging of both eyes
- Assess the subject regarding the inclusion/exclusion criteria
- Query for AEs
- If the subject meets the entry criteria, schedule the subject to return for the Baseline visit, otherwise, exit the subject from the study as a screen failure

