## 8. General Statistical Considerations

### 8.1 Unit of Analysis

The unit of analysis in this study will be the study eye for all safety and pharmacodynamic summaries. The study eye was selected as the eye that meets all the inclusion criteria and none of the exclusion criteria. If both eyes meet the inclusion and none of the exclusion criteria, the eye with the worst visual acuity at baseline will be selected. If both eyes have the same baseline visual acuity, the right eye will be selected as the study eye. Additionally, non-ocular AEs and medical history will be presented at the subject level. Non-study eye safety summaries will also be presented as appropriate.

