### **8.3 Definition of Baseline**

Baseline is defined as the last measurement prior to the administration of study medication. Change from baseline will be calculated as post-baseline visit minus baseline visit.

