### 12.1.1 LOCF AND OBSERVED DATA APPROACH

Values and change from baseline in number of letters read correctly will be summarized using LOCF approach for study eye by visit and cohort using continuous descriptive statistics. Categorical change from baseline will also be summarized for study eye by visit, total and by cohort.

Observed values and change from baseline in number of letters read correctly will be summarized for study eye by visit and cohort using continuous descriptive statistics. Categorical changes from baseline will also be summarized for study eye by visit, total and by cohort.

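### When both eyes qualify, the Day 1 BCVA reading both picks the study eye and serves as its baseline, which builds a small apparent gain into mean BCVA change

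*Protocol*

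**What the plan says.** Three places carry the same rule for a subject whose two eyes both qualify: the protocol synopsis, protocol 4.2 ("the eye with the worst visual acuity at Baseline will be selected") and SAP 8.1 ("the eye with the worst visual acuity at baseline will be selected"). A tie goes to the right eye.

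Protocol 6.2.2 makes Baseline the Day 1 visit and lists BCVA in both eyes ahead of the injection. SAP 8.3 then states: "Baseline is defined as the last measurement prior to the administration of study medication", and "Change from baseline will be calculated as post-baseline visit minus baseline visit". The Day 1 pre-dose BCVA is therefore both the selecting reading and the reference reading.

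An earlier reading exists. At Screening, 3 to 30 days before Day 1, protocol 6.2.1 requires: "Assess BCVA (using the ETDRS protocol with manifest refraction) in both eyes".

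The change score feeds SAP 12.1.1 ("Observed values and change from baseline in number of letters read correctly will be summarized for study eye by visit and cohort"), the LOCF version of the same summary, and the categorical change tables. The overall as-observed and LOCF tables for the full analysis set are marked for the topline delivery. SAP 13.2 uses the same reference for its safety summary and for a flag of worsening by at least 10 letters. The synopsis states that there is no active control arm.

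**The concern.** A BCVA reading is the eye's true level plus short-term error. Taking the lower of two readings tends to pick an eye that has just read below its true level. When that same reading is the baseline, the next reading is expected to be higher even if nothing has changed.

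The direction is fixed: the apparent change in the study eye is positive. It enters both dose groups, every post-baseline visit, and both the as-observed and the LOCF tables. In a controlled trial it would largely cancel between arms. Here the raw mean change is what readers will interpret, so whatever the effect amounts to stays in the result.

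The low baseline also makes the SAP 13.2 worsening flag slightly too rare in study eyes. The mirror image applies to the fellow eye of a two-eye subject, whose baseline is too high on average.

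**Working it through.** The documents give no figure for this effect, so there is none to reproduce.

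**Inputs from the documents.** Selecting reading: Day 1 BCVA (protocol 4.2 and 6.2.2). Reference reading: the same Day 1 BCVA (SAP 8.3). Eligibility range: 31 to 88 letters (inclusion 7).

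**Inputs that are assumptions.** s, the SD of one BCVA reading about the eye's true level: 2 to 5 letters. τ, the SD of the true difference between the two eyes: 0 to 20 letters. f, the share of subjects with two eligible eyes: 0 to 50%.

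**Step 1: effect per two-eye subject.** The difference between the two Day 1 readings has variance τ² + 2s². The covariance of the first eye's error with that difference is s². Given that the first eye reads lower, its expected error is −√(2/π) · s² / √(τ² + 2s²). Later readings carry new error, so the expected apparent gain is

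gain = √(2/π) · s² / √(τ² + 2s²).

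For s = 4 and τ = 10: 0.798 × 16 / √(100 + 32) = 12.77 / 11.49 = 1.11 letters.

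| s | τ = 0 | τ = 5 | τ = 10 | τ = 15 | τ = 20 |
|---|---|---|---|---|---|
| 2 | 1.13 | 0.56 | 0.31 | 0.21 | 0.16 |
| 3 | 1.69 | 1.10 | 0.66 | 0.46 | 0.35 |
| 4 | 2.26 | 1.69 | 1.11 | 0.80 | 0.61 |
| 5 | 2.82 | 2.30 | 1.63 | 1.20 | 0.94 |

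Simulation of 1,000,000 subjects with no true change agreed with the formula in the seven combinations tried. Applying the 31 to 88 range moved the result by less than 0.1 letter (1.17 against 1.11 at s = 4, τ = 10).

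**Step 2: effect on the group mean.** Subjects with one eligible eye contribute nothing, so the shift is f × gain. At s = 4, τ = 10:

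- f = 0: 0
- f = 10%: 0.10 × 1.11 = 0.11 letters
- f = 25%: 0.25 × 1.11 = 0.28 letters
- f = 50%: 0.50 × 1.11 = 0.56 letters

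**Step 3: selecting on Screening BCVA instead.** With independent errors at the two visits, the Day 1 reading of the chosen eye is no longer selected to be low, and the expected gain is 0 (at most 0.07 letters in simulation with the 31 to 88 range applied). If the errors at Screening and Day 1 correlate at r, about a fraction r remains. At s = 4, τ = 10, simulation gave 0.34 letters at r = 0.3 and 0.55 at r = 0.5, against 1.11 under the present rule.

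**The case against.** The strongest reply is that the effect is small and little depends on it. Every input to its size is assumed. To count as a two-eye subject, each eye must separately meet inclusion 4 to 6: recent diagnosis, at least three prior injections, a documented and maintained response, and the latest injection within 42 days of screening. Nothing in the documents suggests that this is common. With 10 subjects per group and an assumed SD of change of 8 to 10 letters, the standard error of the mean is 8/√10 = 2.5 to 10/√10 = 3.2 letters, well above the shift. The primary endpoint is adverse events. There is no hypothesis test, and the SAP calls the study exploratory. The rescue criteria compare with on-study values, so rescue-free status and time to rescue are untouched. CST is not the selecting variable. If the two groups have similar shares of two-eye subjects, the comparison between doses is hardly affected.

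All of this stands, and it limits the point to a minor one. It does not remove it: noise in the mean is no reason to accept an avoidable shift with a known direction.

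A reader might infer three stronger things that the documents do not support:

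- That the reported gain will be inflated by a letter or more. At group level that needs large reading error, nearly equal eyes and a high share of two-eye subjects, all at once.
- That Screening selection abolishes the bias. This holds only for independent errors. The visits may be as little as 3 days apart, and a fluctuation in edema can outlast that.
- That a Day 1 reading could swap the eyes after a screening period of anti-VEGF treatment managed the other way round. Protocol 5.6.2 and 5.6.3 govern medication during the study, and protocol 6.1 places enrolment at the Day 1 dose. No passage says that the eyes are managed differently between Screening and Day 1.

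**Conclusion.** The concern holds in a limited form. In subjects with two eligible eyes, the plan uses one reading both to choose the eye and as its baseline, which gives a positive expected BCVA change without drug effect and with no control arm to subtract it. The mechanism and direction follow from the documents, provided that BCVA readings contain some error. The size does not: about 0.2 to 2.8 letters per two-eye subject over the assumed ranges, and probably a fraction of a letter in a group mean. It is zero if no enrolled subject has two eligible eyes.

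Only BCVA change from baseline and the SAP 13.2 flag are directly affected. The point is worth correcting because correction is cheap. It is not a flaw that undermines the study.

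**What to change.** In the synopsis, protocol 4.2 and SAP 8.1, choose between two qualifying eyes on BCVA at the Screening Visit, right eye if tied. Record the choice before Day 1. Leave SAP 8.3 as it is, so that the Day 1 pre-dose BCVA remains the analysis baseline.

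This needs no new measurement or visit. The costs are small:

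- The non-study eye may occasionally read worse than the study eye on Day 1. Inclusion 8 sets a 53-letter floor for a worse non-study eye and refers to screening and baseline scores together, without saying whether being worse at one visit is enough. That wording should be checked against the new rule.
- Where the ranking of the eyes reverses between the two visits, the rule changes which eye is injected, on a reading up to 30 days old. The clinical team must be content with that.

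If enrolment has started, the rule need not change. Report how many subjects in each group had two eligible eyes, and tabulate BCVA change with and without them.
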